This study's intervention will be referred to as mIVAA. mIVAA is comprised of two components: 1) a digital image capture device for magnification and documentation of the cervix during VIA screening done by midwives staffing La Liga's mobile units. Digital imaging devices used in this study will be the Pocket (device developed at Duke University) and/or digital camera of a mobile phone; and 2) a telemedicine platform that enables two-way communication between midwives and colposcopists (Gynecologist-Oncologist). mIVAA can facilitate visual inspection of the cervix through magnification and documentation for midwives, and allows for remote evaluation of cervical images by a colposcopist to determine the need for follow-up clinical evaluation for women with a positive VIA screen.

mIVAA will be implemented in the mobile units (MUs), with support from 1 to 4 expert colposcopists who work at La Liga detection centers in Lima. In the mobile units, midwives will acquire cervical images using a digital imaging device. The images will be transmitted to an expert colposcopists using a mobile device over cellular/WiFi networks.

We will use an adaptation of an existing telemedicine platform developed by MI&T to facilitate the evaluation of cervical images by colposcopists and communication with providers at mobile units. Women being screened in the mobile units will receive an expert evaluation of their cervical images, a management plan and a follow-up appointment for colposcopy and biopsy, as necessary, will be scheduled. As part of the study, we will assess how soon the evaluation, management plan and follow-up appointment are possible after the cervical cancer screening, i.e., within a few hours, same day, within a week etc. For women without suspected lesions, a referral will be possible as per standard of care once Pap results are available and if positive.

Aim 1: To pilot test mIVAA in a community-based setting in Peru.

Methodology:

For this aim, we will enroll approximately 102 women attending any one of five La Liga mobile units for cancer screening, and approximately 18 La Liga health providers and administrative staff.

As part of the pilot, we will:

- Test the feasibility of integrating mIVAA into the existing workflow at the mobile units.
- Assess mIVAA for image quality, network stability, challenges with image transmission, and ability and time to reach experts and receive feedback from experts (two-way communication between health providers).

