- Once health providers and staff are consented, screened and enrolled, we will work with La Liga to train midwives, nurse technicians who worked in mobile units, and colposcopists to use mIVAA (including use of the Pocket) and on research protocols including maintaining confidentiality of participant

data.

Midwives with assistance from nurse technicians

Activity 1: Use mIVAA system during VIA with consenting women

For each woman who consents to the use of mIVAA system, midwives will:

- Attempt to capture digital images of the cervix with mIVAA.
- Enter relevant clinical notes in mIVAA.
- Use mIVAA to send images of the cervix and of the VIA results form for each patient to participating expert colposcopist for evaluation of these images to evaluate the need for a management plan,
- For women with a positive VIA or suspicion of cancer, follow-up clinical evaluation with a colposcopist in a La Liga detection center will be scheduled based on feedback received from these same colposcopists as per La Liga's institutional protocols.
- For women without suspected lesions, further referrals may be made according to standard of care based on Pap results when available, and if positive.

Activity 2: Provide feedback on mIVAA through a brief survey and interviews, and/or an individual or group interview. Discussions will assess feedback and satisfaction with mIVAA. Individual or group interviews may be completed in person, by phone or by Zoom. The interviews will be audio recorded using an encrypted digital audio recorder, voice recording app on tablet or using Zoom's audio recording function.

Study staff will document in Spanish La Liga provider and staff feedback, and translate to English for analysis and inclusion in any publications. Interviews may be audio recorded, transcribed and translated.

Colposcopists

Activity 1: Use mIVAA system to access patient cervical screening documentation and communicate with midwives and staff at mobile unit.

For each patient, expert colposcopist will:

- Provide feedback on whether the patient should have a follow-up clinical evaluation.
- Rate quality of cervical image.

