Activity 1: Use mIVAA system during VIA for consenting women

- Midwives and nurse technicians will proceed with usual care with all women who register for a cancer screening exam.
- Research staff will provide the nurse technician or midwife with a green card in the medical record that indicates that a woman has consented for the study. Research staff will verify that the name of the patient on the clinical history form/medical record matches the name on the consent.

If an enrolled woman screens positive on the VIA, the midwife will:

- Capture cervical images using mIVAA system.
- Enter relevant clinical notes in mIVAA.
- Use mIVAA to send images of the cervix, VIA result and clinical notes for each patient to participating expert colposcopist for evaluation of these images to evaluate the need for a management plan,
- For women with a positive VIA or suspicion of cancer, follow-up clinical evaluation with a colposcopist in a La Liga detection center will be scheduled

based on feedback received from these same colposcopists as per La Liga's institutional protocols.

If a consented woman screens negative (without suspected lesions or suspicion of cancer) on the VIA or does not have a VIA screen:

- Midwife will document on a screening eligibility form, whether or not she completed a VIA screen for the patient and the VIA result.
- Research staff will inform the woman that she is not eligible for the study, and therefore she will not continue with further activities.
- Further referrals may be made according to standard of care based on Pap results when available, and if positive.

Activity 2: Provide feedback on the use of mIVAA through a survey, brief interviews, and/or an individual or group interview. Discussions will assess feedback and satisfaction with the mIVAA system.

Study staff will document in Spanish La Liga provider and staff feedback, and translate to English for analysis and inclusion in any publications. Interviews may be audio recorded, transcribed and translated.

Colposcopists

Activity 1: Use mIVAA system to access patient cervical screening documentation and communicate with midwives and staff at mobile unit.

For each patient, an expert colposcopist will:

- Provide feedback on whether the patient should have a follow-up clinical evaluation.
- Rate quality of cervical image.

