- Percentage of VIA screened women who are VIA+ (by study arm)
- Average # of days from screening to when a follow-up appointment is scheduled (by study arm)
- Percentage of women who were screened using mIVAA
- Percentage of mIVAA screened women with suspected cancer or pre-cancer by midwife
- Percentage of mIVAA screened women with suspected cancer or pre-cancer by expert
- Average # of days from screening to when expert enters feedback using mIVAA

- Percentage of mIVAA screened women with expert feedback within 0-7 days of mIVAA screening date
- Concordance between midwife and colposcopist on women with suspected cancer or pre-cancer as measured by:
 - Number of women screened positive by midwife
 - Number of women screened positive by expert colposcopist

System outcomes

- Average # of attempts per woman before a readable image is obtained by midwife
- Percentage of mIVAA screened women with at least 1 image rated as readable by expert
- Number of instances of mIVAA failure
- Number of instances of network failure

13. Data & Safety Monitoring:

The risks from participation in the study are considered minimal and commensurate with getting screened with routine methods of cervical cancer screening in Peru such as Pap smears. While no formal data and safety monitoring board is established for this study, study personnel will be instructed to report any unexpected and study-related adverse event to the local study PI in Peru, and Duke PI immediately.

14. Privacy, Data Storage & Confidentiality

Privacy during data collection:

Surveys and interviews will be conducted in mutually agreed upon locations where participants' privacy can be ensured.

Identifying information collected

The study will collect identifying information such as names, dates of birth, and mobile phone numbers to enable the prospective tracking of participants and pulling of medical records. In addition, for women enrolled at the mobile units, data from medical record will be abstracted to measure study outcomes. Mobile phone numbers provided by the participants will be used for any study-related communication.

The study will collect identification information only from health professionals and La Liga personnel, such as participants' names, dates of birth, and mobile phone numbers for reaching out to participants to complete study activities.

Data storage and confidentiality:

Specific actions to maintain confidentiality will include:

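### The colposcopist receives the midwife's VIA result with the images, so midwife-colposcopist concordance is not a comparison of independent readings

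*Combined protocol and SAP*

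**What the plan says.** Section 5, Aim 1 (midwives, Activity 1) covers every woman who consents to mIVAA, whatever her VIA result. The midwife attempts images, enters clinical notes and must "Use mIVAA to send images of the cervix and of the VIA results form for each patient to participating expert colposcopist".

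Section 5, Aim 2 (midwives, Activity 1) restricts imaging to VIA-positive women: "If an enrolled woman screens positive on the VIA, the midwife will" capture images and then "Use mIVAA to send images of the cervix, VIA result and clinical notes for each patient to participating expert colposcopist".

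In both aims the colposcopist's first activity is to "Use mIVAA system to access patient cervical screening documentation and communicate with midwives and staff at mobile unit". Two entries per patient are listed for the expert: "Provide feedback on whether the patient should have a follow-up clinical evaluation", and a rating of image quality.

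Section 12, under secondary process outcomes, lists "Concordance between midwife and colposcopist on women with suspected cancer or pre-cancer as measured by" two counts: women positive according to the midwife, and "Number of women screened positive by expert colposcopist". The same list also has the percentages of mIVAA-screened women with a suspected lesion according to the midwife and according to the expert.

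**The concern.** A concordance figure tells the reader how far two people agree when each judges the same woman. Here the second reader is handed the first reader's answer, and the plan keeps no record of what the second reader would have said from the images alone. Agreement could then reflect what the images show, deference to the midwife's form, or both, and the data could not separate them.

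The expert suspected-lesion percentage comes from the same unmasked reading. At stake is how two descriptive process outcomes can be interpreted.

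**Working it through.** **1. The texts side by side.**
- Sent to the expert in Aim 1: images plus an image of the VIA results form. In Aim 2: images, VIA result and notes.
- Expert's recorded judgement: one follow-up recommendation per patient, made in the system that holds this material.
- Masking, an image-only reading, or a second masked reader: not described anywhere.
- The documents do not say which item the expert opens first. They do not protect the order.

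Lack of independence follows from this. The size of any bias does not: the plan gives no target, precision or sample size for concordance, so there is no stated figure to reproduce.

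**2. What the two planned counts can show.** Aim 1 states that "we will enroll approximately 102 women attending any one of five La Liga mobile units for cancer screening". At the protocol's VIA positivity of about 10%, roughly 10 are midwife-positive. Suppose the expert also calls 10 positive. If these are the same women, agreement is 102/102 = 100%. If none overlap, 20 women are discordant and agreement is 82/102 = 80.4%. Both cases give counts of 10 and 10.

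**3. Illustration of anchoring.** The expert adopts the midwife's call with probability *a*; otherwise the expert agrees on a share *p* of VIA-positive and *q* of VIA-negative women. Assumptions not in the documents: *a* = 0 to 0.5, *p* = 0.3 to 0.7, *q* = 0.95. From the protocol: *m* = 0.10.

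- P = a + (1 − a)p and N = a + (1 − a)q
- Agreement: po = mP + (1 − m)N
- Expert positive rate: e = mP + (1 − m)(1 − N)
- Chance agreement: pe = me + (1 − m)(1 − e)
- Kappa = (po − pe)/(1 − pe)

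For *p* = 0.5, *a* = 0: po = 0.05 + 0.855 = 0.905; e = 0.095; pe = 0.0095 + 0.8145 = 0.824; kappa = 0.081/0.176 = 0.46.

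For *p* = 0.5, *a* = 0.25: P = 0.625; N = 0.9625; po = 0.92875; e = 0.09625; pe = 0.823; kappa = 0.10575/0.177 = 0.60.

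| p | Kappa at a = 0 / 0.25 / 0.5 | Expert positives among 102 (102e) | Confirmed among 200 VIA-positive (200P) |
|---|---|---|---|
| 0.3 | 0.28 / 0.48 / 0.66 | 7.7 / 8.3 / 8.9 | 60 / 95 / 130 |
| 0.5 | 0.46 / 0.60 / 0.73 | 9.7 / 9.8 / 9.9 | 100 / 125 / 150 |
| 0.7 | 0.61 / 0.70 / 0.80 | 11.7 / 11.3 / 11.0 | 140 / 155 / 170 |

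In Aim 1 the expert's count barely moves while kappa moves a good deal, so only paired data would reveal anchoring there. In Aim 2 the expert's count itself moves.

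**4. Aim 2.** Every imaged woman is midwife-positive, so m = 1 and po = pe = e. Kappa is 0 whatever the expert does (for e < 1). Only the share confirmed can be estimated, and selection alone tells the expert what the midwife found.

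**5. Precision in Aim 1.** Take assumed whole numbers: the expert agrees on 6 of 10 positives and calls 5 of 92 negatives positive. Agreement is 93/102 = 91.2%; pe = (10 × 11 + 92 × 91)/102² = 0.8153; kappa = 0.52. The simple large-sample standard error, √[po(1 − po)/(n(1 − pe)²)], is about 0.15, for a 95% interval of about 0.22 to 0.82. The exact 95% interval for 6/10 is about 26% to 88%.

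Moving four discordant women to agreement (8 of 10, and 3 of 92) gives 97/102 = 95.1% and kappa 0.73, inside that interval. The expert's count is 11 both times (6 + 5 and 8 + 3).

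**The case against.** Sharing the result serves the system's purpose. mIVAA is meant to support two-way communication and a decision on follow-up, and an expert making that decision should have all the information. This stands, and is a reason to separate the measurement from the care decision, not to withhold anything from care.

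Concordance is also one descriptive process item with no hypothesis, target or test, and it is not assigned to Aim 1. The stated aims concern feasibility and follow-up attendance. This stands too, and limits the weight of the point.

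A reader might infer more than the documents support:
- **That agreement is inflated by a known amount.** The documents quantify nothing, and an expert could overcorrect. The kappa shifts rest on assumptions, and kappa is not a planned measure. In the whole-number example the two planned counts do not change at all.
- **That concordance is the only comparison of the two readings, or the main evidence that remote review adds information.** Section 12 also lists the midwife and expert suspected-lesion percentages, and no claim about added information or accuracy is stated.
- **That an image-first display would mask the expert in Aim 2.** It cannot, because only VIA-positive women are imaged. It could hide only the notes.

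Finally, an independent Aim 1 estimate would be imprecise with about 10 VIA-positive women. That is true, but does not make an unmasked figure interpretable as independent agreement.

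**Conclusion.** The point holds for the secondary process outcomes. The expert is given the midwife's result together with the images and no prior image-only call is recorded, so planned concordance is not a comparison of independent readings. The expert suspected-lesion percentage shares the weakness. A lean towards agreement is the expected direction but is not shown.

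Its size cannot be derived from the documents. Under the assumptions above, adopting the midwife's call in a quarter of cases raises kappa by about 0.09 to 0.20 (0.61 to 0.70 at *p* = 0.7; 0.28 to 0.48 at *p* = 0.3), and adds 15 to 35 expert-confirmed women among 200 in Aim 2.

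The two aims need different remedies. Aim 1 allows an image-only comparison across VIA-positive and VIA-negative women; Aim 2 does not. A reader might infer that the attendance comparison is compromised as well. Nothing here shows that: the primary outcome and its sample-size calculation do not use concordance. The change is worth making, but the trial's main conclusion does not depend on it.

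**What to change.** **Aim 1.** Have the same expert, in the same session, first view the images only, record a suspected lesion as yes or no, and lock the entry. The platform then shows the VIA form and notes, and the expert gives the feedback used for care with all information, as now. Compute concordance from the locked call and report the paired 2x2 table of midwife against expert, with intervals. The locked entry also supplies an explicit suspected-lesion call, which section 12 needs and the listed expert activities do not name.

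**Aim 2.** Report the share of VIA-positive women confirmed by the expert, state that the reading was unmasked, and do not call it concordance.

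**If the display order cannot be changed,** describe the Aim 1 figure too as unmasked confirmation of the midwife's call.

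**Cost.** One extra field, a display order in a telemedicine platform that is already being adapted, and slightly more reading time. No extra reader is needed. The documents do not cost the platform change, and the added step falls in a workflow whose burden and feedback time are being assessed. Reported agreement may be lower, and the Aim 1 estimate will be imprecise.

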mHealth-supported Telecolposcopy for Cervical Cancer Programs in Low-resource Settings: Evaluation (mIVAA)

NCT04421131

Document Date: May 21, 2021

1. Protocol Title:

mHealth-supported telecolposcopy for cervical cancer programs in low-resource settings: Evaluation

2. Research Abstract

Our long-term goal is to facilitate early cervical cancer prevention and treatment behaviors that are critical for positive clinical outcomes such as reduced cancer progression and increased survival.

The cervical cancer prevention cascade involves several touchpoints. For instance, women screened with visual inspection with acetic acid (VIA) and suspected to have precancerous or cancerous lesions require additional visits with trained ob-gyn specialists/colposcopists who can conduct further clinical evaluation (e.g., using colposcopy or biopsy). In Lima, Peru, our study partners, Liga Contra el Cáncer-Perú (La Liga) use mobile units to provide community-based cervical cancer screening with VIA and/or Pap. In addition, they provide follow-up clinical evaluation at their brick and mortar clinics (detection centers) in Lima for women who are VIA+ and/or Pap+. However, approximately 77% of VIA+ women screened by La Liga in community settings do not present for follow-up clinical evaluation at one of La Liga's detection centers.

To address this issue, we seek to develop and evaluate mIVAA (mobile Inspección Visual con Ácido Acético – Spanish for Visual Inspection with Acetic Acid (VIA). mIVAA is described in the intervention section.

The central hypothesis is that use of mIVAA will increase the proportion of VIA positive women who complete follow-up clinical evaluation compared to VIA positive women in situations in which mIVAA was not used, thus potentially improving cervical cancer treatment and survival rates. The study will collect qualitative and quantitative data to examine the feasibility and preliminary impact of mIVAA on reducing attrition for follow-up clinical evaluations. The primary outcome is the percentage of referred women who are lost to follow-up in intervention versus control arm. Secondary outcomes include provider and patient satisfaction with the mIVAA system, and decisional conflict about follow-up. Multivariable modeling will examine correlates of follow-up.

Research Summary**3. Purpose of the Study:**

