Cervical cancer screening standard of care:

La Liga mobile units are set up close to busy locations (e.g., a market) in pre-selected communities. Screening is offered 9 am-3:00 pm every weekday for 1-2 weeks per community. Women receive Pap, VIA, breast, thyroid and rectal exams and each clinical encounter typically lasts 15 min (see Table 1). La Liga also has two central administrative offices and clinics (detection centers) where cancer-related screening and treatment is offered by health providers including expert colposcopists, and where administrative staff are based. Training has been conducted on use and reprocessing of the Pocket device, however it is not currently in use in clinics.

Currently, if VIA+ (any evidence of whitening after application of acetic acid; determined at the same time as the exam), women are advised during screening that follow-up clinical evaluation with a medical expert (colposcopist) is required, however no referrals for care are made until Pap smear results are received in about 30 days, unless there is a suspicion of cancer. Patient information and the diagnosis is entered into an electronic database at La Liga (WebLiga). La Liga staff contact women who screen positive and are diagnosed with cervical cancer or pre-cancer to schedule follow-up appointments for care, management and treatment. If the woman misses the colposcopy appointment, La Liga staff call to reschedule. After three attempts at rescheduling, the woman is considered lost-to-follow-up.

Table 1: Standard of care and proposed intervention (mIVAA)

Standard of care	mIVAA
Screen with VIA (IVAA) and Pap in MUs	Screen with VIA, Pap and mIVAA (digital imaging device component) in MUs
No expert review	Expert reviews digital images of the cervix remotely using mIVAA's telemedicine component and refers for follow-up appointments for care, management and treatment, if positive
Refer women for colposcopy based on Pap results 3-4 weeks later	For any women not referred already, refer if needed based on Pap results, per standard of care

Perform diagnostic colposcopy and biopsy and treat, if possible, at central La Liga clinic in Lima	Perform confirmatory colposcopy and biopsy and treat, if possible, at central La Liga clinic in Lima
Additional visits to complete treatment, per standard of care.	Additional visits to complete treatment, per standard of care.

Description of intervention and framework for development:

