Activity 2: Provide feedback on the use of mIVAA through a survey, brief interviews, and/or an individual or group interview. Discussions will assess feedback and satisfaction with the mIVAA system. Individual or group interviews may be completed in person, by phone or by Zoom. The interviews will be audio recorded using an encrypted digital audio recorder, voice recording app on tablet or using Zoom's audio recording function.

Study staff will document in Spanish La Liga provider and staff feedback, and translate to English for analysis and inclusion in any publications. Interviews may be audio recorded, transcribed and translated.

Aim 2: To evaluate effectiveness of mIVAA by comparing the attendance for follow-up clinical evaluation among women screened with mIVAA compared to historical data on women referred for follow-up without mIVAA.

Hypothesis: Use of mIVAA will result in a 13.5% increase in the proportion of screen-positive women completing follow-up clinical evaluation, compared to situations where mIVAA is not used.

Methodology:

For this aim, we will enroll approximately 200 VIA+ women attending any one of five La Liga mobile units for cancer screening, and approximately 18 La Liga health providers and administrative staff. As per standard of care, VIA+ women would be referred for follow-up care. Improving attendance of follow-up care is a primary objective of the study.

As part of the evaluation, we will:

- Assess mIVAA for image quality, network stability, challenges with image transmission, ability and time to reach experts and receive feedback from experts (two-way communication between health providers).
- Assess provider feedback and satisfaction from the use of mIVAA
- Document timing of providing women who screen positive on VIA with colposcopist evaluation of cervical images and management plans based on digital cervical images, and follow-up appointment for confirmatory colposcopy and biopsy.
- Collect survey data from women to identify correlates of follow-up.
- Document rate of follow-up care among women who are referred for management and treatment.
- Abstract historical data from medical records including: clinical notes on Pap results; for women who screened positive on VIA, rates of attending follow-up appointments and colposcopist evaluation; and possible reasons for not attending follow-up appointments.

Study activities with enrolled women

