Activity 2: Provide feedback on the use of mIVAA through a survey, brief interviews, and/or an individual or group interview. Discussions will assess feedback and satisfaction with the mIVAA system.

Study staff will document in Spanish La Liga provider and staff feedback, and translate to English for analysis and inclusion in any publications. Interviews may be audio recorded, transcribed and translated.

Medical record abstraction for historical controls

For the control group, data from 200 women who received cervical cancer screening at a mobile unit prior to use of mIVAA will be abstracted from medical records to assess follow-up and correlates of follow-up.

6. Selection of Subjects:

The following groups of participants will be included in the study:

1. Health providers (for aim 1 & 2): Approximately 18 health providers and administrative staff identified in consultation with La Liga will participate in the study, based on the following eligibility criteria.

Inclusion criteria:

- Age 18 or older
- Must be a health provider (Midwives, nurse technicians, expert colposcopists, etc.) or administrative staff working in La Liga clinics and/or staffing the mobile units.
- Agree to be audio recorded

Exclusion criteria:

- Does not understand the study purpose and details
- Is not willing to sign an informed consent

2. Women for Aim 1: Approximately 102 women who are screened for cervical cancer in the mobile units will be approached for participation in the study, based on the following eligibility criteria.

Inclusion criteria:

- Age 18 or older
- Patients coming to the mobile unit for cervical cancer screening
- Willing to allow use of mIVAA during screening with VIA
- Agree to be audio recorded

Exclusion criteria:

- Currently pregnant
- History of hysterectomy
- Does not understand the study purpose and details
- Is not willing to sign an informed consent

3. Women for Aim 2: Approximately 2,000 women will be approached for participation and consented to allow eligibility screening (eligibility criteria listed below) for participation in the study. Approximately 200 women who screen VIA+ will continue their participation in the study.

Inclusion criteria:

- Age 18 or older
- Patients coming to the mobile unit for cervical cancer screening
- Screen-positive on the VIA
- Willing to allow use of mIVAA during screening with VIA
- Agree to be audio recorded

Exclusion criteria:

- Currently pregnant
- History of hysterectomy

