etc.). The difference in the proportion of women attending follow-up clinical visits between the two arms will be calculated to estimate the intervention effect at 5% level of significance level. Baseline covariates will be modeled using multivariable logistic regression to determine patient characteristics associated with loss-to-follow-up. Measures of predictive power (like R-square) and goodness of fit tests (like the Pearson chi-square) will be used to assess the fit of the regression model.

As part of the qualitative analysis plan, we will conduct applied thematic analysis on the observation notes and interview transcripts. Electronic files will be uploaded into QSR NVivo--software that supports coding and finer level re-coding of text data that enables researchers to explore how concepts fit by developing and modifying a hierarchical coding index. Thematic analysis will be conducted via an iterative process of data collection and analysis that utilizes four interrelated steps: reading; coding; data display; and data reduction. The team will use a codebook of a priori, structural codes based on the interview guide, and then a second round of coding, i.e. content coding, will be conducted to identify additional themes, ideas, or concepts. Twenty percent of transcripts will be coded by 2 team members, inter-rater reliability assessed, and discussions held to resolve coding discrepancies. We will create a summary of each interview and look across interviews for commonly named problems and solutions for each step of image acquisition, transfer, and interpretation.

Data will be summarized in the following areas: Core functionality (including expectations, and communication formats), data analytics, storage and availability, (3) Security, hosting and privacy, 4) Mobile delivery platform, 5) Monitoring and maintenance, 6) Hardware, equipment, power and connectivity needs.

In interviews with women in aim 1 and 2, we will assess satisfaction with the (a) overall experience, (b) timeliness of evaluation of cervical images and management, and (c) any barriers to attending future clinical visits.

Evaluation outcomes are summarized in table below.

Primary outcome - Efficacy

- Percentage of referred women who are lost to follow-up in intervention versus control arm

Secondary outcomes - Process

- Percentage of women approached who consented to participate in study
- Percentage of women approached who refused to participate in study

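### Aim 2 does not fix one population for its primary comparison: women are enrolled on a positive VIA, the outcome counts referred women, and referral is formed differently in each arm

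*Combined protocol and SAP*

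**What the plan says.** Three populations appear in the Aim 2 comparison.

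- **VIA+ women.** The central hypothesis in Section 2 concerns completion of follow-up by VIA+ women, "compared to VIA positive women in situations in which mIVAA was not used". The Aim 2 inclusion criteria in Section 6 require "Screen-positive on the VIA". The list of historical data in Section 5, Aim 2, also asks for attendance among women with a positive VIA.
- **Referred women.** The primary outcome in Section 12 is "Percentage of referred women who are lost to follow-up in intervention versus control arm". Aim 2 itself names its comparator as attendance "compared to historical data on women referred for follow-up without mIVAA".
- **Screened women.** The paragraph on historical controls at the end of Section 5 says that "data from 200 women who received cervical cancer screening at a mobile unit prior to use of mIVAA will be abstracted from medical records". It mentions neither VIA result nor referral. Section 6 has no entry for controls, and no start date or selection rule is given.

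The analysis text in Section 12 compares attendance between arms without naming a denominator.

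Referral is described as follows.

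- **Standard of care, Table 1:** "Refer women for colposcopy based on Pap results 3-4 weeks later". The text above the table makes an exception for suspected cancer. It also says that VIA+ women are told at screening that they need follow-up.
- **mIVAA, Table 1:** the expert reviews the images and "refers for follow-up appointments for care, management and treatment, if positive". A second route follows: "For any women not referred already, refer if needed based on Pap results, per standard of care".
- **Aim 2, Methodology:** a positive VIA is said to lead to referral under standard of care. This does not fit Table 1.

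**The concern.** Referral comes after screening, and mIVAA is designed to change how it is decided: the colposcopist gives an opinion on whether each VIA+ woman needs follow-up. If the denominator in each arm is the women who were referred, the two denominators are produced by different rules. Loss to follow-up can then differ between arms although the same share of VIA+ women attend, or look alike although the shares differ.

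At stake is whether the primary result answers the central hypothesis, which is about VIA+ women completing follow-up. The loose control definition adds to this. Without criteria, a window or a selection rule, two abstractors could draw different control groups from the same records.

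**Working it through.** **Inputs from the documents.** 200 women per group, a 13.5-point difference, 80% power, 5% level (Section 12); 77% loss, given for VIA+ women in Section 2 and for referred women in Section 4; VIA positivity of about 10% (Section 5, Aim 2).

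**Assumptions.** Two-sided test. The sample size paragraph states no control rate, so 77% and 70% are both used. The documents give no referral shares, so those below are illustrations.

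**1. The plan's own figure.** For loss rates p1 and p2, with d = p1 − p2 and mean p̄ (equal groups):

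power = Φ[(d − 1.96·s0)/s1], s0 = √[p̄(1−p̄)(1/n1 + 1/n2)], s1 = √[p1(1−p1)/n1 + p2(1−p2)/n2]

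- 77% vs 63.5%: s0 = 0.0457, s1 = 0.0452, (0.135 − 0.0896)/0.0452 = 1.00, power 84%; odds ratio (0.77/0.23)/(0.635/0.365) = 1.92.
- 70% vs 56.5%: power 80%; odds ratio (0.70/0.30)/(0.565/0.435) = 1.80, the stated value.

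The stated size of 200 per group reproduces.

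**2. Loss among referred women when attendance is equal.** Let a share a of VIA+ women attend in both arms, let a share r be referred, and let every attender be among the referred. Then

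loss among referred = 1 − a/r

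At a 77% control rate, a = 0.23 (46 of 200).

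*Table 1 applied to both arms.* VIA+ controls are referred on Pap. VIA+ mIVAA women are referred by the expert or, failing that, on Pap. The mIVAA set is then at least as wide as the control set. With r = 0.70 in controls and 0.90 under mIVAA:

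- controls: 1 − 0.23/0.70 = 67.1%
- mIVAA: 1 − 0.23/0.90 = 74.4%

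mIVAA looks 7.3 points worse with no difference in attendance.

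*All VIA+ controls count as referred (Aim 2 Methodology), while the expert triages the mIVAA arm (Table 1).* Control loss is 77%.

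| mIVAA women unreferred | mIVAA loss | False gain, 77% control rate | False gain, 70% control rate |
|---|---|---|---|
| 10% | 1 − 0.23/0.90 = 74.4% | 2.6 points | 3.3 points |
| 20% | 1 − 0.23/0.80 = 71.3% | 5.8 points | 7.5 points |
| 30% | 1 − 0.23/0.70 = 67.1% | 9.9 points | 12.9 points |

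The last column uses a = 0.30 in the same formula. These are upper limits, because every attender is placed among the referred.

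*All VIA+ women referred in both arms, or referral unrelated to attendance.* The bias is 0.

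**3. Power with all VIA+ women as the denominator.** If the 13.5-point gain holds in all VIA+ women, power is as in step 1. Suppose instead that it holds only among referred mIVAA women, that a share u is unreferred, and that unreferred women count as not completing. Then mIVAA loss = 1 − (1 − p2)(1 − u), against the full control rate:

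| u | 77% control rate: loss, gain, power | 70% control rate: loss, gain, power |
|---|---|---|
| 10% | 67.15%, 9.85 points, 59% | 60.85%, 9.15 points, 49% |
| 20% | 70.8%, 6.2 points, 29% | 65.2%, 4.8 points, 18% |
| 30% | 74.45%, 2.55 points, 9% | 69.55%, 0.45 points, 5% |

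**The case against.** The strongest reply is that the authors use VIA+ and referred for largely the same women. The figures fit: Section 4 gives 10% of screened women referred and 77% of them lost, while Sections 2 and 5 give 77% of VIA+ women lost and about 10% VIA+. VIA+ women under standard of care are told at screening that they need follow-up, and the Aim 2 midwife procedures can be read as scheduling every VIA+ woman. If so, the denominators coincide. This stands as a possible reading, and it is why the bias may be zero. It does not settle the matter: equal percentages do not show that the sets are the same, Table 1 refers controls on Pap, and scheduling under mIVAA depends on the colposcopist's feedback.

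A second reply is that a false gain for mIVAA needs two accounts at once, Aim 2 Methodology for controls and Table 1 for mIVAA. That is correct. A reader might infer that the plan is tilted in favour of mIVAA; the documents do not support this, because Table 1 applied consistently points the other way.

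A third is that Section 4 targets attrition after referral, so loss among referred women is a legitimate outcome. It is, as a secondary one. As the primary outcome it does not match the hypothesis.

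**Conclusion.** The concern holds as a fault of definition. The hypothesis and the mIVAA arm use VIA+ women, the primary outcome uses referred women, and the controls are described in three ways with no criteria, start date or selection rule. Because referral follows screening and is decided differently by arm, a comparison among referred women can be biased. In the illustrations above the result ranges from 7.3 points against mIVAA, through zero, to a false gain of up to 9.9 points (77% control rate), next to a target of 13.5. These are not estimates. They rest on assumed referral shares, equal attendance among VIA+ women, and all attenders being among the referred.

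A reader might also infer from the abstraction paragraph that controls will be unselected screened women, few of them VIA+. The documents do not support that as the intention: the hypothesis, the Aim 2 comparator and the historical data list all point to VIA+ or referred controls. The stated sample size is not in error.

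**What to change.** - **Controls (Section 6).** Define them as 200 VIA+ women who meet the Aim 2 criteria that records can show (18 or older, not pregnant, no hysterectomy), screened at the mobile units in a stated window that ends before the first use of mIVAA, including the Aim 1 pilot, and taken consecutively.
- **Primary outcome (Section 12).** Use the proportion of all VIA+ women who do not complete follow-up clinical evaluation, with the same denominator in both arms. Count every VIA+ woman without a completed evaluation as not completing.
- **Secondary and sensitivity analyses.** Report loss among referred women as secondary, with the number referred out of VIA+ women in each arm. As a sensitivity analysis, exclude women judged not to need follow-up.
- **Consistency (Section 5).** Reconcile the Aim 2 Methodology statement on referral with Table 1 and the standard-of-care text.

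**Cost.** No new patients. If records cannot be filtered electronically by VIA result, finding 200 VIA+ controls takes about 200/0.10 = 2,000 screening records. The main statistical cost is the power loss in step 3 of the working if the gain is confined to referred women. The plan should state that loss and fix the counting rule before abstraction begins.
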